Section 8 Study Objectives	
 Evaluate for hip, thigh, or knee pain, or change in gait from medical history
#17d: Error in Section 9.1, description of Cohort 3 has been corrected to state that at least 17 additional subjects will be randomized	
Section 9.1 Overall Study Design and Plan	Cohort 3 – children aged 0 to < 6 months (n ≥ 20 total: 3 sentinel subjects who receive BMN 111, and at least 20 17 additional subjects randomized 1:1 to treatment or placebo control). Treatment begins at ≥ 3 months to < 6 months after 3 months of observation
#17e: Clarification about age-appropriate dose adjustment has been added to indicate that subjects will be administered the recommended dose appropriate to their current age	
Section 9.1.1 Overall Study Design and Plan Section 9.1.1 Dose Adjustments	As subjects age on study, they will be administered the dose determined to be appropriate for their current age. For example, if a subject enrolls into Cohort 2 at age 20 months, they will receive the recommended dose for subjects aged ≥ 6 to < 24 months until they turn 24 months in age. When they turn 24 months in age, they will begin to receive the recommended dose for subjects aged ≥ 24 to < 60 months.
#17f: The time window for the Week 56 safety follow-up visit has been changed from ± to + 7 days to allow a full 4 weeks between the last dose of study drug and the safety follow-up visit	
Table 9.1.1 Section 12.1.10 Week 56 Safety Follow-up	Week 56 Safety Follow-Up (± + 7d) 12.1.10 Week 56 Safety Follow-up (± + 7d)
#17g: Clarified that the screening/baseline hip assessment includes a pelvis x-ray	
Table 9.1.1 Section 12.1.1 Screening/Baseline Day -30 to Day -1	Screening baseline hip assessment with pelvis x-ray
#17h: Because the definition of ACH-related events differed between sites, capture of ACH-related events	

Section No./Title	Text Revisions
has been changed to capture all procedures listed in the Schedule of Events to ensure all procedures are collected and analyzed	
Tables 9.1.1 and 9.1.2 Section 9.11.6.2	Capture achondroplasia related all procedures in the Schedule of Events 9.11.6.2 Procedures due to Achondroplasia During the Study
Sections 12.1.2-12.1.11; Sections 12.2.2-12.2.3	
 • Capture all procedures

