Rationale: Imaging assessments, excluding MRI, evaluate the safety of BMN-111 by identifying bone pathologies, morphologies, BMD, and BMC. The pelvis X-ray assessment has been removed to reduce the subjects' radiation burden, because the femoral head is captured on X-rays of the lower extremities. DXA of the forearm has also been removed. Thus, concerns regarding excess radiological exposure have been addressed.

3. The MRI assessments remain as a subsection in the Secondary Efficacy Variables section. [9.11.2]

Rationale: MRIs evaluate the effect of BMN 111 on skull and brain morphology, an efficacy variable.

4. The screening baseline hip assessment with pelvis X-ray has been removed from the Schedule of Events [Table 9.1.1]

Rationale: Eliminating the pelvis X-rays at the screening visit will help minimize the radiation burden on study subject.

5. Footnotes have been changed to modify procedures and to add early termination visits (ETV) for anthropomorphic measurements, DXA, and X-rays [Table 9.1.1]

Rationale: The changes in ETV for have been made to align 111-206 with other studies in the clinical program. Changes in the X-ray and DXA procedures also help minimize the radiation burden on the study subjects.

6. The Child Behavior Checklist has been moved from §4.12.3.3 Clinical Outcome Assessments to be a subsection of §9.12.6 Safety Variables [§9.12.6.6]. A sentence specifying that the CBCL should be given prior to other study assessments was added.

Rationale: The CBCL checklist addresses symptoms related to issues of safety (eg, sleep problems, aggressive behavior) rather than efficacy. It is thought that the answers to the CLCL, as a Patient Reported Outcome instrument, may be affected by the study procedures.

7. The following sentence was added to §9.3.3 and §9.3.4 “After completing the observation period, subjects must fulfill the general eligibility criteria prior to receiving treatment with study drug.”

Rationale: Cohort 3 subjects have different eligibility criteria during the observational period, thus Cohort 3 subjects who complete the observation period must also fulfill the general eligibility criteria before receiving treatment.

8. Mention of sterile diluent for reconstitution of BMN 111 has been deleted. [§9.4.2.1]

Rationale: Only sterile water for injection is provided for reconstitution of drug product.

9. The secondary efficacy variables were updated. [§9.12.3]

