Vitamin D, 25-hydroxy test	X												X	
Salivary cortisol	X										X		X	X
Serum prolactin	X										X		X	X
Plasma PK and cGMP assessments ^l		X						X		X	X	X		
Anti-BMN 111 immunogenicity ^m		X				X		X		X		X		X

Procedure ^a	Screening/ Baseline Day -30 to Day -1 ^b	Day 1	Day 2	Day 3	Day 8 (±1d)	Week 3 (±7d)	Week 6 (±7d)	Week 13 (±7d)	Week 20 (±7d)	Week 26 (±7d)	Week 39 (±7d)	Week 52 (±7d)	Week 56 Safety Follow-Up (+7d) ^{aa}	Early Term Visit
Genomic biomarkers (optional) ⁿ	X													
Bone metabolism blood biomarkers ⁿ	X				X		X		X		X			X
Bone metabolism urine biomarkers ^o		X	X	X		X		X		X	X	X		X
BMN 111 PD urine biomarkers ^o		X	X	X		X		X		X	X	X		X
Urine chemistry ^o		X	X	X		X		X		X	X	X		X
Hip monitoring ^p										X		X		X
MRI brain/skull ^q	X											X		X
Sleep study ^r	X											X		X
Clinical outcome assessment: Bayley-III	X									X		X		X
Clinical outcome assessment: Wee-FIM ^s	X									X		X		X
Clinical outcome assessment: ITQOL ^s	X									X		X		X
Safety assessment: CBCL ^s	X									X		X		X
DXA (BMD and BMC) of whole body [less head], spine) ^t	X											X		X ^t
AP and lateral X-rays of spine ^u	X											X		X ^u
AP X-rays of lower extremities ^u	X											X		X ^u
Clinical photographs (optional) ^v	X											X		X

Procedure ^a	Screening/ Baseline Day -30 to Day -1 ^b	Day 1	Day 2	Day 3	Day 8 (±1d)	Week 3 (±7d)	Week 6 (±7d)	Week 13 (±7d)	Week 20 (±7d)	Week 26 (±7d)	Week 39 (±7d)	Week 52 (±7d)	Week 56 Safety Follow-Up (+7d) ^{aa}	Early Term Visit
Capture concomitant procedures/interventions/surgeries													X	X
BMN 111 or placebo administration ^w														
BMN 111 or placebo accountability														X
Adverse events ^x													X	X
Concomitant medications ^y	X												X	X
Phone call ^z														
Home health visit														

^a Clinic visits (except Days 1, 2, 3, and 8) have a ± 7-day window. Anthropometric measurement and imaging assessments can be conducted either pre-dose or post-dose.

^b If the 111-901 visit at which the subject enters Study 111-206 and the 111-206 Screening visit are on the same day, the procedures common to both visits will be performed one time only. All blood tests at Screening visit should be obtained between Day -30 and Day -14.

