- ⁿ For optional genomic biomarkers, if the sample is not collected on Day 1, it may be drawn at any time during the study. The sample will be used for exploratory genomics including, but not limited to, NPR-B, BRAF, and other genes associated with CNP signalling. Bone metabolism blood biomarkers will be waived at screening for subjects weighing $<$ 7.0 kg to limit the blood volume on the smallest subjects at this visit. Serum samples for bone metabolism biomarkers will be collected pre-dose on the indicated visits. Bone metabolism blood biomarkers include bone-specific alkaline phosphatase and collagen type X.
- ^o Urine biomarkers and urine chemistry (urine creatinine test) should be obtained pre- and post-dose (approximately 2-4 hours after study drug administration) for subjects when possible at the indicated visits. The time of collection will be recorded. Urine biomarkers include cGMP and C-terminal telopeptide of cross-linked collagen type II (CTX-II).
- ^p Hip monitoring: this assessment will include medical history of the hip and physical exam to determine changes in hip function or pain with hip range of motion. Adverse changes from baseline will trigger further evaluation.
- ^q MRI is obtained at the early termination visit only if the previous assessment was done more than 3 months prior to early termination (unless additional study is recommended by Investigator, BioMarin, or DMC). Efforts to obtain a satisfactory image can be discontinued after 3 unsuccessful attempts.
- ^r If sleep study is uninterpretable, subject may need to repeat assessment. Obtained at the early termination visit only if the previous assessment was done more than 3 months prior to early termination (unless additional study is recommended by Investigator, BioMarin, or DMC).
- ^s Wee-FIM is waived for children $<$ 6 months old; CBCL is waived for children $<$ 18 months old. ITQOL and CBCL should be performed before any other assessments during the study visit.
- ^t Efforts to obtain a satisfactory image can be discontinued after 3 unsuccessful attempts. DXA will be obtained at ETV only if subject discontinues after 9 months to reduce unnecessary radiation exposure (unless additional scans are recommended by investigator, BioMarin, or DMC).

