26. Have abnormal findings on baseline clinical hip exam or imaging assessments that are determined to be clinically significant as determined by the Investigator
27. Have a condition or circumstance that, in the view of the Investigator, places the subject at high risk for poor treatment compliance or for not completing the study
28. Have any concurrent disease or condition that, in the view of the Investigator, would interfere with study participation or safety evaluations, for any reason

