9.12.6.10 Hip Clinical Assessment

The hip clinical assessment should be completed by an appropriately qualified physical therapist or a physician (MD) i.e., the investigator or the sub-investigator at the time points indicated in the Schedule of Events (Table 9.1.1 and Table 9.1.2). Medical history will be obtained to evaluate for hip, thigh, or knee pain, or change in gait. The physical exam (including observation of gait when possible) identifies and evaluates any changes in hip function or pain with assessment of active and passive range of motion. Changes from baseline may trigger further evaluation based on the investigator's clinical assessment, which may include hip imaging and/or orthopedic consultation. If findings on clinical hip exam are determined to be clinically significant by the investigator and in consultation with Sponsor's Medical Monitor and orthopedic specialist (if needed), the DMC will be notified of AEs resulting from clinically significant abnormal hip monitoring assessments. DMC may provide recommendations as to if/when BMN 111 or placebo treatment should be temporarily or permanently discontinued.

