12.1 Treatment Visit(s)

12.1.1 Screening/Baseline Day -30 to Day -1

- Medical history
- Parental height
- Diagnostic genetic testing to confirm achondroplasia (if needed)
- Physical examination
- Weight
- Vital signs
- Electrocardiogram
- Echocardiogram
- Anthropometric measurements
- Clinical laboratory assessments (hematology, chemistry, urinalysis)
- Thyroid function tests
- Vitamin D, 25-hydroxy test
- Salivary cortisol
- Serum prolactin
- Genomic blood biomarkers (optional)
- Bone metabolism blood biomarkers
- MRI brain/skull
- Sleep study
- Clinical outcome assessment: Bayley-III
- Clinical outcome assessment: Wee-FIM
- Clinical outcome assessment: ITQOL
- Safety assessment: CBCL
- DXA
- AP and lateral X-rays of spine

- AP X-rays of lower extremities
- Clinical photographs (optional)
- Concomitant medications

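### Under Amendment 2 the dedicated clinical hip assessment has no Screening visit, yet an exclusion criterion and the hip follow-up rules still rely on a baseline hip exam

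*Protocol*

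**What the plan says.** All references are to the protocol as amended by Amendment 2 (8 February 2019) unless stated otherwise.

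**What is scheduled.** In Table 9.1.1 the row "Hip monitoring" is marked at Week 26, Week 52 and Early Termination and nowhere else. The visit lists in Sections 12.1.7, 12.1.9 and 12.1.11 agree. The screening list, "12.1.1 Screening/Baseline Day -30 to Day -1", contains no hip item, and Table 9.1.2 (Cohort 3 observation period) has no hip row.

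**What presumes a baseline.**
- Exclusion criterion 26 in Section 9.3.2 (number 25 in the synopsis) excludes children who "Have abnormal findings on baseline clinical hip exam or imaging assessments that are determined to be clinically significant".
- Footnote p to Table 9.1.1: "Adverse changes from baseline will trigger further evaluation".
- Section 9.12.6.10 describes a physical exam that "identifies and evaluates any changes in hip function or pain with assessment of active and passive range of motion". It says that changes from baseline may lead to further work-up, and it leaves the timing to the two schedule tables.

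**How the gap arose (history only).** The Amendment 1 log had recorded "Clarified that the screening/baseline hip assessment includes a pelvis x-ray". Item 4 of the Amendment 2 summary states "The screening baseline hip assessment with pelvis X-ray has been removed from the Schedule of Events", with the rationale "Eliminating the pelvis X-rays at the screening visit will help minimize the radiation burden on study subject".

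**The concern.** A criterion that turns on a baseline exam, and a rule that turns on change from baseline, both need that exam to be done before the first dose. The schedule that sites follow does not ask for it. The amendment's rationale speaks only of radiation, which a clinical examination does not involve, so the exam appears to have been lost along with the X-ray rather than dropped on purpose.

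The hip matters in this programme. Evaluating hip function, and hip, thigh or knee pain or a change in gait, are secondary objectives (Section 8). The clinical hip assessment is a listed safety outcome to be summarized by treatment group and cohort (synopsis; Section 14.2). The nonclinical risk summary (Section 7.5.1) reports femoral head deformity, acetabular dysplasia and limited hip use as exaggerated responses to the drug. Under Section 10.3.1.7 a pre-existing condition becomes an adverse event only if it worsens, so classifying a hip finding at Week 26 depends on what was recorded before dosing.

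**Working it through.** No formula applies. The check sets the current passages side by side.

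**Step 1. Count the scheduled dedicated hip assessments.** Before dosing there are none in Table 9.1.1, Section 12.1.1 or Table 9.1.2. After dosing starts there are three possible occasions: Week 26, Week 52 and Early Termination. The first planned one falls at 26 of 52 weeks, halfway through treatment. The table and the visit lists agree, so this is not an artefact of a broken table.

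**Step 2. Sort the hip provisions by whether they refer to a baseline.**

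| Provision | Refers to baseline? |
|---|---|
| Exclusion criterion 26 (9.3.2) | Yes, a baseline clinical hip exam or imaging |
| Footnote p, Table 9.1.1 | Yes, adverse change from baseline |
| Section 9.12.6.10 | Yes, change from baseline |
| Individual and cohort hip stopping criteria (9.1.2) | No, clinically significant adverse findings |

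Three provisions need a baseline. The stopping criteria do not.

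**Step 3. Ask whether other Screening items supply it.**
- Medical history (Section 9.8) covers knee, thigh, hip or groin pain and changes in gait or activity. This matches the history part of the later hip assessment, although footnote c to Table 9.1.1 does not repeat it.
- Physical examination (Section 9.10) includes the musculoskeletal system, and its screening results serve as baseline. It does not specify the hip, hip function or range of motion.
- AP X-rays of the lower extremities are taken at Screening, and the Amendment 2 summary says they show the femoral head. They give an imaging baseline but do not measure function or range of motion.

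Symptoms and anatomy are therefore covered in part. The structured exam of hip function and of active and passive range of motion, by the assessors named in Section 9.12.6.10, is not.

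**Step 4. Ask who is affected.** The Amendment 1 visit list had the screening hip assessment, so subjects screened under that text should have it. The document does not say how many had been screened by February 2019. The affected number is thus some unknown part of about 70.

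**Step 5. Ask whether randomization removes the problem.** It protects the comparison between arms. It does not help classify a finding in an individual child, nor in the sentinels, who receive BMN 111 without a concurrent control: 3 cohorts × 3 = 9 at minimum (Section 9.1).

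**Step 6. A related mismatch.** Footnote p makes further evaluation mandatory after an adverse change from baseline. Section 9.12.6.10 makes it optional and subject to the investigator's assessment.

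**The case against.** The strongest reply is that a hip baseline does exist. History, musculoskeletal exam and X-rays are all taken at Screening. Clinically significant screening abnormalities are recorded as pre-existing conditions (Section 10.3.1.8). A physical exam is repeated at every clinic visit, so Week 26 is the first dedicated hip exam but not the first musculoskeletal exam. Exclusion criterion 26 leaves significance to the investigator and admits imaging as well as an exam, so it can be applied. The protocol defines no hip score and plans only descriptive summaries.

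Most of this stands and limits the point. It does not close the gap: nothing requires the general exam to assess hip range of motion or function, so a later restriction may have nothing comparable to be set against.

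Three stronger readings are tempting, and the documents do not support them.
- A reader might infer that the hip stopping criteria lack their reference point. They are worded on clinically significant adverse findings and never mention baseline. At most, a missing exam makes it harder there to tell a new finding from an old one.
- A reader might infer that no subject has a baseline, so that change can be computed for nobody. Subjects screened under Amendment 1 should have had the assessment, and the number screened later is not given.
- A reader might infer that exclusion criterion 26 is inoperable. The remaining screening items allow a judgment; what is missing is the scheduled exam that the criterion names.

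**Conclusion.** The inconsistency is real and lies wholly within the current text. Three provisions rely on a baseline hip exam that neither schedule table nor the screening list contains. For subjects screened under Amendment 2, the missing element is the structured pre-dose record of hip function and range of motion; symptoms, gait and femoral head imaging are partly covered. The consequences are weaker attribution of individual hip findings, least protected in the nine or more sentinels, and room for sites to apply exclusion criterion 26 differently. Neither the primary endpoint nor the randomized comparison is biased by it.

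This rests on two assumptions: that sites do what the schedule and visit lists say, and that no manual or eCRF outside this document restores the exam at Screening. It should be corrected promptly, because a pre-dose exam cannot be obtained once dosing has begun.

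**What to change.** Reconcile Table 9.1.1 and Section 12.1.1 with exclusion criterion 26, footnote p and Section 9.12.6.10. The direct way is to list the clinical hip assessment, without pelvis X-ray, at Screening/Baseline before the first dose, with the same content as at Weeks 26 and 52. Cohort 3 subjects who enter through the observation period would have it at the treatment-phase Screening visit.

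Summarize change from that baseline descriptively by arm and cohort, for example as a shift from normal or abnormal at baseline to each later visit, with sentinels shown apart as the synopsis already plans. Where a subject was dosed without the exam, report the hip baseline as missing rather than reconstructing it from the general physical exam.

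In the same edit, reconcile the mandatory wording of footnote p with the discretionary wording of Section 9.12.6.10. Which of the two applies is for the sponsor's clinical team to decide.

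The cost is a few minutes of non-invasive examination at a visit that already includes a full physical exam, plus one schedule line and one eCRF line. It adds no radiation, so the stated purpose of the Amendment 2 change is kept.

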Table 9.1.2: Schedule of Events Observational Period for Cohort 3 (infants between birth and < 3 months old)

Assessments	Screening ^a	Day 1 ^a (Month 0)	3 Months (± 10 days)
Informed consent	X		
Medical history, including growth history and ACH related history	X		
Concomitant medications	X	X	X
Physical examination ^b	X		
Vital signs ^c	X	X	X
Anthropometric measurements ^d		X	X
Vitamin D, 25-hydroxy ^e	X		X
Alkaline phosphatase ^e	X		X
Bone metabolism blood biomarkers	X		X
Bone metabolism urine biomarkers	X		X
Genomic biomarkers (optional) ^f		X	
Weight		X	X
Body mass index (calculated)		X	X
Clinical outcome assessment: Bayley-III ^g		X	
Clinical outcome assessment: ITQOL ^g		X	
Capture concomitant procedures/interventions/surgeries		X	X
Adverse events ^h	X	X	X

^a Screening and Day 1 (Month 0) assessments may be performed on the same calendar day at the discretion of the investigator. If Screening and Day 1 (Month 0) are done on the same day, vital signs are taken only once. Please refer to eCRF Completion Instructions.

^b A complete physical examination will be performed at Screening. Complete physical exam includes major body systems, including assessment of general appearance; CV; dermatologic; head, eyes, ears, nose, and throat; lymphatic; respiratory; gastrointestinal (GI); musculoskeletal; and neurological/psychological and genitourinary.

^c Vital signs will be measured with appropriate blood pressure cuffs for achondroplasia children following detailed instructions in Study Reference Manual. At screening, blood pressure should be taken with subject in a supine position, after the subject has been resting for at least 5 minutes. At all other visits, blood pressure should be taken one time after at least 5 minutes of rest, with subject in a supine position. Heart rate should be taken at each time point that blood pressure is measured. Left brachial arm should be the first method of assessment considered, and the same site should be used for blood pressure measurement in each subject throughout the study. The method and site of blood pressure measurement will be recorded and should be utilized consistently throughout the remainder of the study.

- d Growth parameters (anthropometric measurements) may include but are not limited to height, standing height, sitting or supine height, weight, upper and lower arm and leg length, and arm span. Body proportion measurements may include but are not limited to upper:lower body segment ratio, upper arm:forearm length ratio, upper leg:lower leg length ratio, and arm span:standing height ratio. Refer to the Anthropometric Measurement Guidelines for specific instructions regarding the collection of growth measurements. All age-appropriate physical measurements will be collected at approximately the same time each visit (± 2 hours) by a trained study staff member; every effort will be made to have the measurements collected by the same study staff member, if possible, throughout the study. Each measurement will be taken in triplicate (excluding weight, taken once).
- e Vitamin D (25-hydroxy) and alkaline phosphatase will be measured during Screening and at the 3-month visit.
- f If sample is not collected at Day 1, it may be drawn at any time during the study. The sample will be used for exploratory genomics including, but not limited to, NPR-B, BRAF, and other genes associated with CNP signaling.
- g Bayley-III is waived for subjects < 1 month old; ITQOL is waived for subjects < 2 months old.
- h AEs will be collected at screening. For subjects enrolled in Cohort 3 (0 to <6 months old), the collection period for all AEs begins after informed consent is obtained.

